### **7.5.1 Primary Efficacy Endpoint**

The primary efficacy endpoint is a composite endpoint defined as the proportion of treated subjects with HBV DNA  $< 50$  IU/mL (approximately 300 copies/mL) and HBeAg seroconversion (HBeAg negative and HBeAb positive) at Week 48 on treatment. Response rates are presented by treatment regimen with a difference in proportions (ETV - PBO), 95% CI and p-value using  $NC = F$ . The difference in proportions and p-value are presented only at Week 48 for the Primary Cohort at the primary analysis (see [Sections 6.3 and 9](#)).

A sensitivity analysis using  $NC = M$  presents response rates.

Another sensitivity analysis using  $NC = F$  presents response rates by imputing successes for subjects randomized to PBO who are missing the primary efficacy endpoint and started rescue open-label ETV before or at Week 48, i.e., (start date of rescue open-label ETV - first dose date of study therapy + 1)/7  $\leq 54$  (see [Sections 8.4 and 8.9](#)).

The proportions of subjects with HBV DNA  $< 50$  IU/mL and HBeAg seroconversion are also summarized at baseline and each scheduled on-treatment visit through Week 48 by treatment regimen. Response rates are presented using  $NC = F$  and  $NC = M$ .

The primary efficacy endpoint is also summarized using  $NC = F$  and  $NC = M$  by treatment regimen and subgroups to examine consistency of effect. Subgroups may include, but are not limited to, the following:

- Age randomization strata (see [Section 7.3.4](#))
- Gender (male, female)
- Baseline HBV DNA ( $< 8 \log_{10}$  IU/mL,  $\geq 8 \log_{10}$  IU/mL)
- Baseline ALT ( $\leq 2 \times$  ULN,  $> 2 \times$  ULN)
- Geographic region (Asia, Europe, North America, South America)
- HBV genotype (e.g., A, B, C, D, E, etc.)
- Route of transmission (mother-to-child transmission; household/close contact exposure; transfusion; sexual contact; IV drug use; other)

Subgroup categories may be combined based on the availability of data.

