4.1.2 Subjects Experiencing Significant Elevations Of ALT Due To Acute Exacerbation of CHB

A subject who experiences an extreme elevation of ALT due to acute exacerbation of CHB should be carefully managed at the discretion of the primary investigator. Additional laboratory testing and frequent clinical evaluations are recommended (See [Figure 5.3.2.1](#)).

- An extreme elevation of ALT due to acute exacerbation of CHB is defined as:
 - a serum ALT > 1,000 U/L,OR
 - an elevation in serum ALT > 20x ULN WITH associated clinical or laboratory findings suggestive of hepatic dysfunction,
- Upon investigator request and after discussion and approval by the BMS Central Medical Monitor:
 - A subject who experiences an extreme elevation of ALT due to acute exacerbation of CHB will be provided access to rescue open-label ETV.

The choice of anti-HBV therapy to be used to treat an extreme elevation of ALT due to acute exacerbation of CHB remains at the discretion of the investigator. Only open-label ETV will be provided by the sponsor, and will be limited to those subjects who do not have access to acceptable alternative anti-HBV therapy. Subjects started on rescue open-label ETV will be provided the drug for up to 96 consecutive weeks. Upon completion of the rescue open-label ETV course, subjects will remain on study as part of the LTFU phase until they complete a total of 5 years of study participation from the start of blinded treatment or 48 weeks beyond the completion of rescue open-label ETV; whichever is later. During this time, subjects may be treated with alternative anti-HBV therapy at the discretion of their primary investigator. The sponsor reserves the right to terminate access to rescue open-label ETV if any of the following occur: a) the study is terminated due to safety concerns; b) the subject can obtain medication from a

government sponsored or private health program; or c) therapeutic alternatives become available in the local market.

Specific decisions regarding the management of an extreme elevation of ALT due to acute exacerbation of CHB remain at the discretion of the subject's primary investigator but access to rescue open-label ETV must be discussed with and approved by the BMS Central Medical Monitor.

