5.3.2 Other Guidance

5.3.2.1 Study Subject Management for ALT Elevations or Hepatic Clinical Events

Acute exacerbation of hepatitis B (ALT > 2 x baseline AND > 10 x ULN) and hepatic clinical events may represent a critical scenario with the potential for serious hepatic injury and death. Guidelines for managing these events can be found in [Figures 5.3.2.1](#). Should an event as described occur, a blood sample for HBV DNA determination using a sensitive PCR technique should be obtained and sent to the central laboratory for this study. If results are needed urgently for patient management decisions, a sample should be also drawn and concurrently sent to a local laboratory for assessment. An unscheduled visit laboratory kit should be used for the HBV DNA sample if it is collected at a time that is not required by the protocol. Non-HBV related potential causes of worsening hepatitis also need to be considered (hepatitis A, C, D, concomitant medications, etc).

Figure 5.3.2.1: Management of Significant Elevations of Serum ALT Due to the Acute Exacerbation of Chronic Hepatitis B

¹ Clinical manifestations suggestive of hepatic complications include but are not limited to: Ascites, Hepatic encephalopathy, Increasing nausea, vomiting, or abdominal pain, Jaundice, Variceal bleeding, etc.

² Laboratory findings that may be suggestive of evolving liver dysfunction include but are not limited to: Increasing INR, Total bilirubin, or Serum lactate levels, or Declining serum albumin values.

³ Subjects experiencing acute exacerbation of CHB resulting in ALT flare WITH clinical or laboratory findings suggestive of liver dysfunction or other serious safety concern may be eligible for rescue open-label ETV as determined on a case-by-case basis following consultation with the BMS Central Medical Monitor.

⁴ Labs may be processed by local or central laboratory. An unscheduled visit laboratory kit should be used if labs are collected at a time that is not required by the protocol.

⁵ Subjects placed on rescue open-label ETV will be immediately placed into the study's LTFU phase. Protocol visits should be scheduled as described in Section 6.1. Patients who are provided rescue open-label ETV to treat an extreme elevation of ALT due to acute exacerbation of CHB should undergo additional non-protocol visits and assessments at the discretion of the managing investigator. See section 4.1.2.

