### 5 SAMPLE SIZE AND POWER

One hundred and twenty-three (123) subjects (randomized 2:1 to ETV vs placebo) in this study provide 90% power to show superiority of ETV versus PBO assuming a response rate for the primary endpoint HBV DNA by PCR < 50 IU/mL (approximately 300 copies/mL) and HBeAg seroconversion of 20% for ETV and 1% for PBO. A two-sided significance level of 0.05 is used. Subjects who either discontinue from study treatment prior to Week 48 or have having missing Week 48 HBV DNA or HBeAg serology measurement are considered as failures at Week 48 (Non-Completer = Failure). The efficacy estimate for ETV is derived from an analysis of the identical endpoint (HBV DNA by PCR < 300 copies/mL and HBeAg seroconversion) in the pivotal Phase 3 study of HBeAg-positive subjects, (AI463022). The efficacy estimate for PBO is derived from evidence in the literature which shows that whereas spontaneous seroconversion occurs at a relatively high rate in children, viral replication remains detectable using sensitive PCR assays. The results of the Gilead Sciences' pediatric CHB study (GS 518) support this estimate; 3 of 57 placebo treated subjects (5.3%) achieved HBeAg seroconversion, but only 1 of 58 subjects (1.7%) achieved HBV DNA < 2.23 log10 copies/mL at Week 48.

This sample size also fulfills the requirement that the ETV integrated pediatric safety database has at least 100 pediatric subjects who have received ETV for at least 48 weeks; this database will be comprised of subjects currently enrolled in study AI463-028 and from this study (AI463-189).

Currently 24 nucleoside naive subjects are enrolled in AI463-028; all 24 would have had 48 weeks of safety data collection by the time study AI463-189 reaches Week 48.

Based on the original planning for study AI463-189, it is estimated that 175 subjects will be enrolled to have approximately 123 subjects randomized (approximately 30% screen failure rate). Randomization is 2:1 (ETV 82: PBO 41); assuming a 10% drop out rate per year and even enrollment for 2 calendar years, approximately 72 ETV randomized subjects will have 48 weeks of safety data by study Week 144. This brings the number of subjects that will be included in the integrated safety database at the end of study Week 144 to approximately 96 subjects.

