## 6 STUDY PERIODS, TREATMENT REGIMENS AND POPULATIONS FOR ANALYSES

### 6.1 Study Periods

Study periods for efficacy and safety analyses are defined as follows:

- **Pre-treatment period** begins at the first visit until initiation of study therapy.
- **On-treatment period** begins after the first day of study therapy and ends at the last dose of study therapy plus 5 days.
- **ETV treatment period** begins after the first day of active ETV and ends at the last dose of active ETV plus 5 days.
- **Off-treatment follow-up period** begins on the last dose of study therapy plus 6 days and ends at the start of alternative anti-HBV therapy minus 1 day.
- **Long-term follow-up period** begins on the last dose of study therapy plus 6 days until the end of the study.
- **Alternative ETV follow-up period** begins on the later of the last dose of study therapy plus 6 days and the start of alternative ETV therapy, until the end of the study.

Note that rescue open-label ETV is considered alternative anti-HBV therapy. See [Section 8.9](#) for additional conventions.

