- Dose end date of active ETV is the dose end date of study therapy for ETV-randomized subjects and the dose end date of open-label ETV for PBO-randomized subjects. This date is used to assess time on active ETV.
- Last dose date of active ETV is the dose end date of active ETV derived only when the last dose date of study therapy is not missing.
- Start date of rescue open-label ETV is the earliest start date of rescue open-label ETV identified from valid dosing records, ie, non-missing start date and total dose > 0, from rescue open-label ETV study medication CRFs.
- Start date of alternative ETV therapy is the earliest start date of (1) rescue open-label ETV, or (2) concomitant ETV taken on treatment or during long-term follow-up.
- Start date of alternative anti-HBV therapy is the earliest start date of (1) rescue open-label ETV, or (2) concomitant anti-HBV medication taken on treatment or during long-term follow-up.
- Last contact date is the death date, if it exists, or the latest of the following dates: randomization; first or last dose of study therapy; adverse event onset or resolution; hepatitis B related diagnosis; laboratory test (safety, pregnancy, serology and virology); liver biopsy; physical measurement; physical exam; neurologic exam; vital sign; non-study medication start or stop; last contact from end of treatment or end of study subject status; Tanner staging.

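### The rescue sensitivity analysis in SAP 7.5.1 covers only sponsor-supplied rescue ETV, so a placebo child rescued with non-sponsor anti-HBV therapy stays a failure in it

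*SAP*

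**What the plan says.** **Primary rule.** SAP 7.5 scores any treated child with missing Week 48 data as a failure (NC = F), whatever the reason.

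**Rescue sensitivity analysis.** SAP 7.5.1 adds an analysis that presents response rates after "imputing successes for subjects randomized to PBO who are missing the primary efficacy endpoint and started rescue open-label ETV before or at Week 48". Timing is set by the rescue open-label ETV start date: (start date − first dose date + 1)/7 must not exceed 54. SAP 7.5.2.1 to 7.5.2.4 apply the 7.5.1 analyses to the four Week 48 key secondary endpoints.

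**Who gets rescue open-label ETV.** Protocol 4.1.2 leaves the choice of therapy for an extreme ALT elevation to the investigator. The sponsor supplies only ETV, and that supply "will be limited to those subjects who do not have access to acceptable alternative anti-HBV therapy". A footnote to Protocol Figure 5.3.2.1 begins "Subjects placed on rescue open-label ETV will be immediately placed into" and names the LTFU phase. It speaks only of rescue open-label ETV.

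**How the SAP classes these therapies.** SAP 6.1 notes that rescue open-label ETV counts as alternative anti-HBV therapy. SAP 8.9 derives one start date for that class: the earlier of rescue open-label ETV and "concomitant anti-HBV medication taken on treatment or during long-term follow-up". The date closes the off-treatment follow-up period (SAP 6.1) and enters time in off-treatment follow-up (SAP 7.4.1). No Week 48 efficacy rule uses it.

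**On-treatment period.** SAP 6.1 says it "begins after the first day of study therapy and ends at the last dose of study therapy plus 5 days".

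**The concern.** The sensitivity analysis asks what happens if placebo children who needed rescue are scored as responders and not as failures. Its trigger is tied to the supplier of the drug, not to the event or to the start of active therapy. Two placebo children with the same flare, both off blinded drug and both without a Week 48 value, are scored differently according to whether an acceptable alternative was available to them. The child on sponsor ETV becomes a success and the child on non-sponsor therapy stays a failure. Every child left out keeps the placebo rate lower than a full version of the analysis would, so the result looks more robust in ETV's favour than it has been shown to be.

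A smaller question arises when blinded drug continues alongside non-sponsor anti-HBV therapy. Nothing in the SAP ends the on-treatment period at the start of that therapy, so a Week 48 value obtained on it is credited to the randomised arm.

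**Working it through.** **1. The plan's own figure.** Inputs from SAP 5: "A two-sided significance level of 0.05 is used"; the design is said to "provide 90% power to show superiority of ETV versus PBO assuming a response rate"; the rates are "HBeAg seroconversion of 20% for ETV and 1% for PBO"; allocation is 2:1 (82 ETV, 41 placebo). With pooled variance under the null and no continuity correction:

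- p̄ = (0.01 + 2 × 0.20)/3 = 0.1367
- n(placebo) = [1.960 × √(0.1367 × 0.8633 × 1.5) + 1.282 × √(0.01 × 0.99 + 0.20 × 0.80/2)]² / 0.19² = (0.825 + 0.384)² / 0.0361 ≈ 40.5, so 41
- ETV = 2 × 41 = 82, total 123, power 90.4%

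The stated sample size reproduces. Nothing below changes it.

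**2. Three placebo children set side by side.** Each has a flare before Week 48.

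| Course | Primary analysis (NC = F) | Rescue sensitivity analysis |
|---|---|---|
| A. Blinded drug stopped, rescue open-label ETV, endpoint missing | failure | success |
| B. Blinded drug stopped, non-sponsor therapy, endpoint missing | failure | failure |
| C. Blinded drug continued, non-sponsor therapy, Week 48 value present | as observed | as observed |

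A and B differ only in the last column. A child in A or B who already had an on-treatment value in the Week 48 window (over 42 to 54 weeks) before stopping would be scored on that value, so not every rescued child has a missing endpoint.

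**3. Size of the A/B difference.** One placebo child is 1/41 = 2.4 points, against an assumed placebo rate of 1% (0.01 × 41 = 0.4 children expected). Take 16/82 = 19.5% as an illustrative ETV rate (0.20 × 82 = 16.4), no other placebo success, and m children on course B. The documents give no value for m; 0 to 3 is an assumption.

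| m | Placebo rate with B left as failures | Placebo rate with B imputed as successes (m/41) | ETV − placebo after imputation |
|---|---|---|---|
| 0 | 0% | 0% | 19.5 points |
| 1 | 0% | 2.4% | 17.1 points |
| 2 | 0% | 4.9% | 14.6 points |
| 3 | 0% | 7.3% | 12.2 points |

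The rates are unstratified; the SAP combines age strata with CMH weights.

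**4. Course C.** Protocol 5.5.1 does not permit agents active against hepatitis B on study, but Protocol 4.2.3 does not list starting one among the reasons for mandatory discontinuation. SAP Appendix 1 records prohibited medication as a relevant deviation and attaches no consequence for response status. SAP 8.4 selects values within the study period, and that period runs to last dose of study therapy plus 5 days. The value therefore stands. It counts as a primary response only if HBV DNA < 50 IU/mL and HBeAg seroconversion are both met.

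**The case against.** The strongest reply is that this is a gap in one supplementary analysis and no more. That largely stands. A reader might infer that the Week 48 rules as a whole deal only with sponsor rescue ETV. They do not: NC = F makes any child with missing Week 48 data a failure, so courses A and B are alike in the primary analysis.

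A reader might also infer that one or two omitted children could decide significance. With 16/82 ETV responders, an unstratified Mantel-Haenszel test gives p = 0.010, 0.031 and 0.079 for 1, 2 and 3 placebo successes. But SAP 7.5.1 plans only response rates for this analysis, with no test. At three successes the unpooled standard error gives p = 0.041, and the count is assumed. These values illustrate fragility and support no claim about the trial's conclusion.

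A third inference is that Week 48 values may be taken after the Week 52 switch to open-label ETV, because the window runs to 54 weeks. Protocol Table 6.1 schedules no HBV DNA, serology or chemistry at Week 52. With ± 5 days, scheduled draws fall no later than about 48.7 weeks (48 + 5/7) and then no earlier than about 59.3 weeks (60 − 5/7). If an unscheduled sample exists, SAP 8.7 takes the result closest to Week 48. That reading is not supported.

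Course C needs prohibited use, continued blinded drug and, for the primary endpoint, a full composite response. Using the value as observed is also a recognised treatment-policy approach. In the placebo arm it works against ETV, so forcing such values to failure in the primary analysis would remove placebo responders and favour ETV. This is a good reason to leave the primary analysis alone.

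**Conclusion.** The point holds for the rescue sensitivity analysis. It omits placebo children who stop study drug for non-sponsor anti-HBV therapy and have no Week 48 value, although the SAP places both kinds of therapy in one class and already derives a start date covering both. The omission favours ETV, by 2.4 points of the placebo rate per child in a Primary Cohort of 82:41.

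The number of such children is unknown and may be zero. Non-sponsor therapy follows from the access restriction for children who have an alternative, but the documents do not support calling it the usual route. The purpose of the sensitivity analysis is inferred from its construction. Protocol Figure 5.3.2.1 is not reproduced in the text reviewed and may say more about blinded drug during a flare.

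Course C is a secondary point. The SAP uses the value as observed in either arm, and a supplementary analysis is enough to show whether that matters.

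**What to change.** 1. In SAP 7.5.1, and through it in 7.5.2.1 to 7.5.2.4, replace the condition of having started rescue open-label ETV, and its start date, with having started alternative anti-HBV therapy and the SAP 8.9 start date for it. Keep the 54-week limit. Keep the restriction to missing endpoints, so that no observed Week 48 value is overwritten with a success.
2. Add a supplementary analysis, applied equally to both arms, in which Week 48 values obtained on or after that date while blinded drug continues are treated as missing, and so as failures under NC = F. Leave the primary analysis unchanged.

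The cost is SAP wording and reuse of an existing derived date; no new data, visits or subjects are needed. The downside of item 1 is that the sensitivity result may be slightly less favourable to ETV. The SAP 8.9 date does not record why therapy was started, so the rule would also take in placebo children with missing endpoints who began anti-HBV therapy for a reason other than an extreme flare. That errs in the conservative direction.

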### **7.5.2 Key Secondary Endpoints**

The tests of the key secondary endpoints are conducted sequentially in the order specified below, provided the test result of the primary endpoint is significant. The  $n$ th key secondary endpoint is tested provided the test result of the  $(n-1)$ st key secondary endpoint is significant ( $n = 1, 2, \dots, 5$ ).

Treatment regimens are compared (ETV - PBO) with a difference in proportions and p-value at Week 48 on treatment for the Primary Cohort at the primary analysis (see [Sections 6.3](#) and [9](#)) using  $NC = F$ , unless specified otherwise.

#### **7.5.2.1 HBV DNA Below 50 IU/mL**

Analyses described in [Section 7.5.1](#) are performed for the proportions of subjects with HBV DNA  $< 50$  IU/mL on treatment.

#### **7.5.2.2 ALT Normalization**

Analyses described in [Section 7.5.1](#) are performed for the proportions of subjects with ALT normalization ( $ALT \leq 1 \times$  ULN) on treatment.

#### **7.5.2.3 HBV DNA Below LOQ**

Analyses described in [Section 7.5.1](#) are performed for the proportions of subjects with HBV DNA  $< LOQ$  on treatment.

#### **7.5.2.4 HBeAg Seroconversion**

Analyses described in [Section 7.5.1](#) are performed for the proportions of subjects with HBe seroconversion on treatment.

#### **7.5.2.5 Sustained HBeAg Seroconversion During Off-Treatment Follow-up**

Response rates of HBeAg seroconversion are presented by treatment regimen at EOD (end of dosing) and each scheduled visit during off-treatment follow-up through Week 192 using  $NC = F$

and NC = M for the Year 2 Efficacy Cohort with HBeAg seroconversion at EOD. Rates using NC = F are shown only through off-treatment follow-up Week 48.

Treatment regimens are compared between treated subjects with HBeAg seroconversion at both on-treatment Week 48 and EOD (ETV S48 - PBO S48; NC = F) with a difference in proportions and p-value at off-treatment follow-up Week 24 at the final analysis, provided the test result of HBeAg seroconversion was significant at the primary analysis (see [Section 9](#)).

Sustained HBeAg seroconversion is summarized analogously with response rates using NC = M for the Post-Year 1 Efficacy Cohort with HBeAg seroconversion at EOD.

Sustained HBeAg seroconversion at off-treatment follow-up Week 24 is also summarized by subgroups for treated subjects with HBeAg seroconversion at EOD (see [Section 7.5.1](#)).

